Appendix 2 12-Week Safety Follow-Up (Part 1, OLE) Schedule of Assessments

Part 1 (OLE)	Week (± 7 days)		Unscheduled Visit ^c
	6 ^a	12/Early Withdrawal Visit ^b	
Concomitant medications	x	x	x
Adverse events	x	x	x
Urine pregnancy test ^d		x	
Partial physical examination		x	
PK sampling (serum)		x	
Anti-therapeutic antibody sample (serum) ^e		x	
PML neurologic examination ^f		x	

ATA= anti-therapeutic antibody; PK= pharmacokinetic; PML= progressive multifocal leukoencephalopathy.

- ^a Week 6 study assessments are to be made by telephone call and not by clinic visit.
- ^b If the patient discontinues prior to completion of the 12-week safety follow-up, the indicated assessments for the 12-week safety follow-up clinic visit should be performed as the early termination visit of the safety follow-up period.
- ^c Unscheduled visit for safety monitoring.
- ^d For women of childbearing potential, including those who have had a tubal ligation, perform a urine pregnancy test; if the urine pregnancy test result is positive, confirm with a serum pregnancy test.
- ^e If serum sickness or a clinically significant allergic drug reaction is suspected, Sponsor should be notified and serum for etrolizumab PK and ATAs should be drawn and sent to the central laboratory. ATA samples may be used for PK and/or exploratory PD assessments.
- ^f PML neurologic examination consists of the PML Subjective Checklist and the PML Objective Checklist. Administer before other assessments as per [Appendix 5](#).

Appendix 3

Extended Progressive Multifocal Leukoencephalopathy Safety Monitoring (Part 2, SM) Schedule of Assessments

Part 2 (SM)	92-week Extended PML Monitoring Period ^a	
	24, 48, 68, and 92 Weeks after Patient Discontinuation from Study OR Symptom-Driven Unscheduled Telephone Call ^b OR Early Termination ^c	Unscheduled Visit ^d
PML Subjective Checklist (telephone only)	x	
PML Objective Checklist ^e		x
Adverse event reporting to the Sponsor ^f	x	x

OLE-SM= open-label extension–safety monitoring; PML = progressive multifocal leukoencephalopathy.

Note: The extended PML monitoring period is to be conducted for patients completing or discontinuing from OLE-SM Part 1 AND for patients entering OLE-SM Part 2 from blinded Phase III studies after completion of 12-week safety follow-up in the Phase III studies AND for patients entering OLE-SM Part 2 from the Phase II OLE study (GA27927).

- ^a The total length of the PML monitoring period is 104 weeks after the patient discontinues from the study (12-week safety follow-up plus 92-week extended PML monitoring period). The extended PML monitoring period telephone calls will occur at the indicated timepoints for the 92-week extended PML monitoring period. The extended PML monitoring will be conducted using a PML Subjective Checklist over the telephone. PML monitoring should occur within 7 days of the specified day.
- ^b Unscheduled telephone call represents a call that is not as per Schedule of Assessments and it is symptom driven.
- ^c If the patient discontinues after the 12-week safety follow-up visit but prior to study completion (end of extended PML monitoring period), the early termination visit from the extended PML monitoring period should be performed (a subjective checklist by telephone).
- ^d Unscheduled visit represents a visit that is not as per Schedule of Assessments and it is symptom driven.
- ^e If there are any signs or symptoms suggestive of PML identified on the subjective checklist during the telephone call, the patient will be asked to come into the clinic for a neurologic examination, including administration of the PML Objective Checklist.
- ^f Investigators are not required to actively monitor patients for adverse events; however, if he or she becomes aware of any other serious adverse events that are believed to be related to prior study drug treatment, these should be reported directly to Roche or its designee either by faxing or by scanning and emailing the Serious Adverse Event/Adverse Event of Special Interest Reporting Form with use of the fax number or email address provided to the investigators. The investigator may become aware of such events at these timepoints or via other means, but the data are not to be collected routinely.

Appendix 4

Childbearing Potential, Pregnancy Testing, and Contraception

All women of childbearing potential (including those who have had a tubal ligation) will have a urine pregnancy test prior to administration of study drug at subsequent visits. If a urine pregnancy test result is positive, study drug will not be administered that day. The result must be confirmed by a serum pregnancy test (conducted by the central laboratory). Refer to Section 5.5.3 of the protocol for management of a patient with a confirmed pregnancy.

All female patients are considered to be of childbearing potential unless they meet one of the following criteria:

- The patient has been postmenopausal (non–therapy-induced amenorrhea) for at least 12 months
- The patient had a surgical bilateral oophorectomy (with or without hysterectomy) more than 6 weeks prior to enrollment
- The patient had a hysterectomy

Female patients of reproductive or childbearing potential who are unwilling to use a highly effective method of contraception or remain abstinent during the treatment period and for at least 24 weeks after the last dose of study drug will be excluded from study participation.

Abstinence is acceptable only if it is in line with the preferred and usual lifestyle of the patient. Periodic abstinence (e.g., calendar, ovulation, symptothermal, or postovulation methods) and withdrawal are not acceptable methods of contraception.

Examples of highly effective contraception include the following:

- Combined oral contraception pill
- Contraceptive transdermal patch
- Intrauterine device
- Implants for contraception
- Injections for contraception (with prolonged release)
- Hormonal vaginal device
- Sterilization, surgical tubal ligation
- Sole sexual partner consisting of surgically sterilized male partner with appropriate postsurgical verification of the absence of spermatozoa in the ejaculate
- Double-barrier methods: condom **and** occlusive cap (diaphragm or cervical/vault caps) **with** spermicidal foam/gel/film/cream/suppository (Note: a female condom and male condom should not be used together because friction between the two can result in either product failing)

Appendix 4 Childbearing Potential, Pregnancy Testing, and Contraception (cont.)

Patients may provide verbal confirmation that the partner completed appropriate follow-up after vasectomy. Sites are not required to obtain partner medical records.

For men: agreement to remain abstinent (refrain from heterosexual intercourse) or use contraceptive measures and agreement to refrain from donating sperm, as defined below:

With female partners of childbearing potential or pregnant female partners, men must remain abstinent or use a condom during the treatment period and for at least 24 weeks after the last dose of study drug. Men must refrain from donating sperm during this same period.

For men and women: The reliability of sexual abstinence should be evaluated in relation to the duration of the clinical trial and the preferred and usual lifestyle of the patient. Periodic abstinence (e.g., calendar, ovulation, symptothermal, and postovulation methods) and withdrawal are not acceptable methods of contraception.

Appendix 5

Mayo Clinic Score Measurement

Mayo Clinic Score (MCS) is a composite endpoint with four components. The score ranges from 0 to 12 with higher scores indicating more severe disease.

The Mayo Clinic components are as follows:

STOOL FREQUENCY

0 = Normal number of stools for this patient

1 = 1 to 2 stools more than normal

2 = 3 to 4 more stools than normal

3 = 5 or more stools than normal

Subscore 0–3

RECTAL BLEEDING

0 = No blood in stool

1 = Streaks of blood with stool less than half the time

2 = Obvious blood with stool most of the time

3 = Blood alone passed

Subscore 0–3

ENDOSCOPY

0 = Normal or inactive disease

1 = Mild disease (erythema, decreased vascular pattern, mild friability)

2 = Moderate disease (marked erythema, lack of vascular pattern, friability, erosions)

3 = Severe disease (spontaneous bleeding, ulceration)

Subscore 0–3

PHYSICIAN'S GLOBAL ASSESSMENT

0 = Normal (Subscores are 0)

1 = Mild disease (Subscores are mostly 1s)

2 = Moderate disease (Subscores are 1 to 2)

3 = Severe disease (Subscores are 2 to 3)

Subscore 0–3

Appendix 5 Mayo Clinic Score Measurement (cont.)

DATA COLLECTION REQUIREMENTS

Data will be collected on e-diary and other electronic media; during conversion to these media the format of the questions may change.

- A CRITICAL DATA POINT TAKEN AT BASELINE FROM THE PREVIOUS STUDY IS THE PATIENT'S NORMAL NUMBER OF STOOLS. This is defined as the number of stool passed when a patient is in remission/not in flare. This is to be taken from the most recent available data in the patient's medical notes or taken during patient interview at screening in the Phase II and Phase III controlled study.
- Normal number of stools is to be rounded up (e.g., normal number of stools = 1–2 would be rounded to 2).
- The NORMAL number of stools is to be recorded on the e-diary and made visible to the patient to assist with their scoring relative to this number.

NOTE: Data recorded during bowel preparation procedures and day of endoscopy are to be ignored (bowel preparation and endoscopy procedure days are to be loaded onto the e-diary by the patient and excluded from the MCS calculation).

1. Stool frequency

- Stool frequency is to be recorded during the study in the e-diary. E-diary entries are to be made daily during the initial 12 weeks. After the 12-week visit, the stool frequency component of the partial Mayo Clinic Score (pMCS; performed every 12 weeks) and MCS (for the Week 108 assessment) will be collected daily for 4 weeks prior to clinic visit.
- The stool frequency is to be compared with the patient's normal stool frequency and is entered as a score between 0 and 3 (see 1 above) (e.g., a patient normally has 1 stool per day and today has 4 stools; therefore, the patient has 3 stools more than "normal," which yields a value of 2 for that day).
- The stool frequency will be defined as the passage of solid or liquid fecal material. Episodes of incontinence count. A non-productive trip to the bathroom or the simple passage of gas DO NOT COUNT as stool.
- The stool frequency value for endpoint assessment will be calculated as the average (rounded to the nearest integer) from the three most recent stool frequency scores that were entered in the e-diary prior to the clinic visit (and prior to endoscopy) and prior to the days devoted to bowel preparation and endoscopy.

2. Rectal bleeding

- Rectal bleeding is to be recorded during the study in the e-diary. E-diary entries are to be made daily during the initial 12 weeks. After the 12-week visit, the rectal bleeding component of the pMCS (performed every 12 weeks) and MCS (for the Week 108 assessment) will be collected daily for 4 weeks prior to clinic visit.

Appendix 5

Mayo Clinic Score Measurement (cont.)

- The rectal bleeding score is to be categorized from 0–3 according to the definition given in 2 above.
- The rectal bleeding value for endpoint assessment will be determined by the worst of the three most recent rectal bleeding scores that were entered in the e-diary prior to the clinic visit and prior to the days devoted to bowel preparation and endoscopy.
- Patients are to be instructed to ignore any blood which is caused by menstruation or hemorrhoids.

3. Endoscopy Subscore

- This score is provided by the local endoscopy reading as a subscore of 0 to 3.
- Findings on endoscopy will be documented by photographic evidence.
- The score will be based upon the worst affected segment visualized (up to and including the descending colon).

4. Physician's Global Assessment

The physician's global assessment WILL:

- Be based on the patient's overall status
- Reflect how the patient is doing at present. Assessment SHOULD NOT reflect past disease severity or complexity or the number/kinds of medicines the patient is receiving

Be based on the:

- Rectal bleeding score, stool frequency score, and endoscopic evaluation
- Patient's recollection of abdominal discomfort and general sense of well-being
- Patient's performance status, fecal incontinence, and mood
- Physician's observations and physical exam findings
- Reflect disease activity NOT disease severity (e.g., do not automatically give a high PGA to patients with pancolitis or severe/complicated disease or patients requiring multiple medications)

The physician's global assessment will be provided by the Investigator as a score of 0 to 3 and entered into the tablet.

Appendix 5 Mayo Clinic Score Measurement (cont.)

CALCULATION OF THE MAYO CLINIC SCORE

1. Mayo Clinic Score assessment will be performed at Week 108 and at early withdrawal if the early withdrawal visit occurs prior to Week 108, as outlined in the protocol Schedule of Assessments.
2. MCS Remission
MCS \leq 2, a rectal bleeding score of 0, physician's global assessment of 0–1, stool frequency subscore of 0–1, endoscopy score of 0–1
3. Endoscopic remission
Endoscopic subscore = 0

PARTIAL MAYO CLINIC SCORE

The pMCS is identical to the MCS BUT EXCLUDES THE ENDOSCOPY SUBSCORE

- Timepoints for pMCS can be found in the protocol Schedule of Assessments
- pMCS is also required if a patient experiences disease worsening

E-DIARY MALFUNCTION OR LOSS

The help desk for the e-diary vendor (CRF Health) should be contacted in the event of e-diary malfunction or loss. Until a working e-diary can be provided to the patient, site staff should, after the e-diary malfunction or loss, retrospectively collect the previous day's stool frequency and rectal bleeding subscores from the patient via telephone interview within the next working day following the e-diary failure or loss. These data will then be transcribed into a data clarification form within CRF Health's TrialManager system for approval.

REFERENCE

Appendix 6 Worksheet for the PML Neurologic Examination

PML SUBJECTIVE AND OBJECTIVE CHECKLISTS OF NEUROLOGIC ASSESSMENTS TO MONITOR FOR PROGRESSIVE MULTIFOCAL LEUKOENCEPHALOPATHY (PML) IN THE ETROLIZUMAB PHASE III STUDIES

PML usually manifests with subacute, progressive neurologic deficits including:

Neurologic Domain	Signs/Symptoms	Relevant PML Subjective/Objective Checklist Question
Altered mental status	Can encompass a variety of presenting signs and symptoms including cognitive changes (confusion, difficulty concentrating, memory loss) and altered behavior (including personality changes)	Q2, Q5, Q6
Higher cortical dysfunction	Impaired comprehension and/or formulation of language (aphasia), loss of ability to recognize objects, persons, sounds, shapes, or smells (agnosia)	Q2, Q5, Q6
Visual changes	Loss of visual fields (homonymous hemianopsia), double vision (diplopia)	Q1
Motor deficits	Weakness (hemiparesis or monoparesis), seizures (generalized or partial), difficulties with speech (dysarthria) or swallowing (dysphagia)	Q2, Q3
Sensory deficits	Sensory loss (i.e. paresthesia)	Q7
Coordination	Difficulty walking and maintaining balance (ataxia), lack of voluntary coordination of limb movement (limb ataxia)	Q4

In order to monitor patients for PML, a neurologic exam (including evaluation of cranial nerves, motor and sensory function, coordination, and mental status) will be performed as per the schedules of assessments (see [Appendix 1](#) and [Appendix 2](#)). This neurologic exam will consist of administration of the PML Subjective Checklist and the PML Objective Checklist.

At screening, the PML Subjective Checklist and the PML Objective Checklist (including the components listed as optional, e.g. muscle group strength testing, recall of 3 objects in 1 minute, and sensory testing) should be performed.

At all other visits, the PML Subjective Checklist and the PML Objective Checklist (bolded items) should be performed, and the optional items should only be performed when there is an abnormal finding on the corresponding PML Subjective Checklist (i.e. complaints of focal weakness or focal sensory change would prompt a more detailed objective neurologic evaluation).

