5.2 SAFETY PLAN (PART 2 SAFETY MONITORING)

PML Monitoring Part 2 (SM)

Following the 12-week safety follow-up period in either the Phase II OLE or Phase III controlled studies or in Part 1 (OLE) of the OLE-SM, all patients are to continue to be monitored for PML for an additional 92 weeks (extended PML monitoring) in Part 2 (SM) of this study, providing a total of 2 years PML follow-up after the last dose of study drug. No etrolizumab will be administered during this time.

PML monitoring during this period will consist of the PML assessment interview conducted by telephone at intervals of approximately 6 months. If there are any signs or symptoms suggestive of PML identified on the subjective checklist during the telephone call, the patient will be asked to come into the clinic for a neurologic examination, including administration of the PML Objective Checklist (see Appendix 3). Any signs or symptoms suggestive of PML or cases of suspected PML (see Appendix 6) should be documented, handled, and expeditiously reported to the sponsor as adverse events of special interest or serious adverse events, as appropriate, within 24 hours, as described in Sections 5.1 and 5.3.3, and Appendix 7 (PML algorithm). Study site personnel and patient participants will be educated regarding the signs and symptoms of PML and

suspected cases of PML will be managed as in Section 5.1. Patients are to be instructed to contact the investigator immediately if they experience signs and/or symptoms suspected to be PML between the 6-month telephone intervals.

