Appendix 6 Worksheet for the PML Neurologic Examination (cont.)

PML Subjective Checklist

Symptoms	“Compared to how you usually feel, have you had a significant change in any of the following?”		If the answer is “Yes”, obtain a description of the symptom(s) with examples	Applicable Objective Test(s): Document result on PML Objective Checklist Worksheet
	YES	NO		
1. Have you been experiencing any persistent difficulty with your vision such as loss of vision or double vision? Have you been having trouble with reading?				
 • Test visual fields and ocular motility
2. Have you been experiencing any persistent difficulty speaking or having your speech understood by others?				
 • Casual observation of speech output for dysarthria or aphasia.
3. Have you been experiencing any persistent weakness in an arm or a leg?				
 • Test for pronator drift (Barre maneuver). • Assess gait. • Test muscle strength (only if indicated).
4. Have you noticed yourself regularly bumping into things or having difficulty writing?				
 • Observe tandem gait and finger to nose.
5. Have you regularly been experiencing difficulty understanding others?				
 • Test ability to follow serial commands.
6. Have you had persistent problems with your memory or thinking?				
 • Recall of 3 objects over 1 minute with distraction (only if indicated).
7. Have you been experiencing any persistent numbness or other loss of sensation?				
 • Test sensation side to side with either pinprick or cold (only if indicated).

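### No PML checklist question asks about seizures or swallowing, although Appendix 6 lists both as PML signs, and in Part 2 the telephone checklist is the only scheduled screen

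*Protocol*

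**What the plan says.** Protocol Appendix 6 opens with a table of how PML usually presents, one row per neurologic domain, with a last column headed "Relevant PML Subjective/Objective Checklist Question". Three rows matter here:

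- Motor deficits: "Weakness (hemiparesis or monoparesis), seizures (generalized or partial), difficulties with speech (dysarthria) or swallowing (dysphagia". The column points to questions 2 and 3.
- Altered mental status: "cognitive changes (confusion, difficulty concentrating, memory loss) and altered behavior (including personality changes". The column points to questions 2, 5 and 6.
- Higher cortical dysfunction, which includes "loss of ability to recognize objects, persons, sounds, shapes, or smells (agnosia". The column again points to questions 2, 5 and 6.

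The Subjective Checklist in the same appendix has seven questions. Question 2 reads "Have you been experiencing any persistent difficulty speaking or having your speech understood by others", question 3 "Have you been experiencing any persistent weakness in an arm or a leg" and question 5 "Have you regularly been experiencing difficulty understanding others". Question 6 is about memory or thinking. The other three cover vision and reading (1), bumping into things and writing (4), and numbness or loss of sensation (7).

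For Part 2, Section 5.2 states: "PML monitoring during this period will consist of the PML assessment interview conducted by telephone at intervals of approximately 6 months". Appendix 3 places the calls at Weeks 24, 48, 68 and 92. Under Sections 4.4.2 and 5.2, a finding on the telephone checklist brings the patient to the clinic for the Objective Checklist. Section 3.3.3 gives Part 2 a single outcome measure, the incidence of suspected or confirmed PML.

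**The concern.** The appendix names signs that it wants monitored and points to questions that do not ask about them. In Part 1 this matters less, because the questions are one of several active checks. In Part 2 the questions are the scheduled check. A patient whose only new sign is a seizure or trouble swallowing can truthfully answer No seven times, and the call then does not lead to an examination.

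What is at stake is the completeness of Part 2's only outcome. A case that is not found lowers the count, which is the reassuring direction, and a case found later is worked up later.

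**Working it through.** No figure in the plan is to be reproduced here. The check sets the signs in the Appendix 6 table against the wording of both checklists.

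| Sign in the table | Questions cited | Subjective Checklist | Objective Checklist |
|---|---|---|---|
| Seizures | 2, 3 | Not asked; question 2 is speech, question 3 limb weakness | No item |
| Swallowing difficulty | 2, 3 | Not asked | No item; the detailed speech instructions mention poor control of saliva, but as a feature of dysarthria |
| Altered behaviour or personality | 2, 5, 6 | Not named; question 6 (thinking) may draw it out | No item |
| Loss of recognition | 2, 5, 6 | Not named; questions 5 and 6, or the reading part of question 1, may draw it out | No item; three-object recall tests memory and is done only on complaint |

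A keyword search of the seven questions for each of these four signs returns no match. The other listed signs each match a question: vision 1, speech 2, weakness 3, coordination 4, comprehension 5, memory and confusion or concentration 6, sensation 7.

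The wording adds a difficulty for seizures. All seven questions are framed around persistent or regular difficulty (the added reading question in item 1 is the exception), which suits an episodic event poorly.

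Next, what else in Part 2 would find such a sign:

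- Scheduled: only the telephone checklist (Sections 5.2 and 5.3, Appendix 3). The intervals between calls are 48 − 24 = 24, 68 − 48 = 20 and 92 − 68 = 24 weeks, and no call follows Week 92.
- Adverse events: not actively monitored. Non-PML serious events are reported if the investigator learns of them and believes them related to study drug (Section 5.4.2).
- Concomitant therapy: need not be recorded (Section 4.2.1.1), so a newly started anticonvulsant would not show in the data.
- Not scheduled: the instruction to contact the investigator between calls (Section 5.2), symptom-driven calls and visits (Appendix 3), and alert cards for patients and caregivers (Section 5.1.1.1.1).
- Escalation: Appendix 7 acts on a subjective abnormality with its corresponding objective abnormality, or on high clinical suspicion. A presentation with seizures alone has only the second route.

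Part 1 differs. Adverse events are sought at each contact by open questions (Sections 5.4.1 and 5.4.3), and the required objective items are performed at every scheduled PML examination whatever the patient answers (Appendices 1 and 6).

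**The case against.** The strongest reply has four parts.

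First, the table's last column is a cross-reference by domain and covers both checklists. It does not promise a question for each sign. That is right, so this is a gap in coverage with a loose cross-reference rather than a flat contradiction. But neither checklist has an item for seizures or swallowing, so the reference to questions 2 and 3 leads nowhere for those two signs.

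Second, the call is not limited to seven answers. Section 5.3 says that signs or symptoms suggestive of PML, with reference to Appendix 6, are documented during the calls, and site staff are trained on them. This stands in part: a sign that the patient volunteers will be handled. It does not make anyone ask.

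Third, the unscheduled routes are real, and a caregiver holding an alert card is a plausible source for a seizure or a change in personality. This also stands. These routes need the patient or someone close to start them, and patients may not notice their own change in behaviour.

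Fourth, PML is described as progressive, so a case missed at one call may show an asked-about sign at the next. A case is lost only if it keeps to unasked signs and also reaches no unscheduled route. That limits the likely loss, though it does not remove the delay or the lack of any call after Week 92.

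A reader might infer that the screen cannot detect any of the four signs, or that the PML count is materially biased. The documents support neither. Questions 5 and 6 may elicit behaviour change and loss of recognition, other routes exist, and nothing in the documents says how often PML presents with these signs alone. Nor is a share of unasked signs informative: the denominator depends on grouping (about 15 if each sign is listed singly) and says nothing about frequency.

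**Conclusion.** The point holds for seizures and swallowing, which neither checklist covers. It holds in weaker form for personality change and loss of recognition, which are covered at most indirectly. In Part 2, detection of these signs rests mainly on spontaneous reporting, symptom-driven contact and clinical suspicion. Any error is toward a lower count of suspected or confirmed PML; its size cannot be estimated from the documents.

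The reach is at most about 2100 patients, the ceiling in Section 6.1 rather than an enrolled number. No planned test or estimate changes: Protocol Section 6.4 describes Part 2 PML events in listings and narratives, and the SAP covers Part 1 only. The conclusion assumes that the calls use the seven questions as printed in Appendix 6.

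**What to change.** Reconcile the checklist with its own table. Keep the seven questions unchanged, so that earlier and later calls remain comparable on them. Add lines on new seizures and on difficulty swallowing, and preferably on change in behaviour or in recognising people or objects, noticed by the patient or by others. Correct the table's last column to match.

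Use the revised form at the remaining calls and give the date of change when Part 2 is reported. The SAP puts last Part 1 dosing at 15 May 2022. Follow-up of 12 + 92 = 104 weeks from that date runs to about May 2024. If no calls remain, correct the table and state in the Part 2 report that seizures and swallowing were not asked about.

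The cost is a short form revision, slightly longer calls and a few more false-positive call-backs. The change also alters ascertainment partway through follow-up and departs from the form shared with the Phase III studies, which is why its date should be reported.
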